1 BACKGROUND

Treatment of younger patients between 30-50 years of age with knee osteoarthritis is a challenging treatment problem for physicians. The younger, active population has different expectations for management of osteoarthritis with a strong desire to maintain their physical activities and quality of life. Ideally, treatments for osteoarthritis in these patients that can allow them to maintain their activity levels and provide clear future health benefits of regular exercise are preferred. There is a lack of effective treatment for individuals including surgical options with mild osteoarthritis outside of physical therapy exercises, oral analgesic medications, and steroid injections which have possible negative side effects and short durations of symptom improvement. Hylan G-F 20 in a single injection form can provide analgesic benefit up to 6 months and can be used as a treatment in younger patients not improving with traditional treatments.¹

1.1 Overview of Non-Clinical Studies

Preclinical investigations have demonstrated that Hylan G-F 20 can favorably affect chondrocyte metabolism and recent clinical studies [Ann Rheum Dis. 2004 May; 63(5):478-82; Osteoarthritis Cartilage. 2005 Mar;13(3):216-24] provide support for a disease-modifying effect of Hylan G-F 20 therapy. An evaluation of the non-clinical tests by FDA was based in large part on the previous device approval (for three injections). There were no unresolved safety issues.

1.2 Overview of Clinical Studies

Studies in populations with osteoarthritis of the knee demonstrate that after 3 or more years of follow-up, individuals have worsening of limitations in activities.² In one study 48.7% of limitations (n= 405) participants with knee symptoms were classified as experiencing a poor two-year outcome using a dichotomous outcome measure of activity.³ Prognostic factors for worsening of limitations in activities include increased pain, reduced ROM, and decreased muscle strength at 1-year follow-up; higher morbidity count; and to a lesser extent poor cognitive functioning. Continuing exercise is important, as there are numerous health benefits for reducing chronic diseases such as hypertension, diabetes and obesity. While osteoarthritis is also a chronic disease, it is focal in nature whereas lack of exercise can result in increased incidence of systemic chronic diseases that have more detrimental health effects and health care costs.⁵ A single injection preparation of hylan G-F 20 (6 mL) has shown improvement over placebo in a double blind randomized control trial.¹ Hylan G-F 20 has demonstrated improvements with repeated treatment of knee osteoarthritis using a series of three 2 mL preparations⁴; however, the effectiveness of repeated injections of the 6 mL is not yet known. Maintaining activity levels and pain tolerance are important in the younger age group as this translates to continuing good mobility and ability to work.

A randomized, double-blind, saline-controlled, multicenter trial of 253 patients (mean age 63 years) with moderate to severe OA knee pain. Most had radiographically confirmed Kellgren-Lawrence grade II or III OA at baseline. Patients initially received arthrocentesis and then either one 6-mL injection of Synvisc-One or one 6-mL injection of placebo (saline). Follow-up visits occurred at weeks 1, 4, 8, 12, 18, and 26. The primary end point

was the difference between the groups in the change from baseline in patient-assessed pain as measured by the WOMAC A score (average of 5 questions) over 26 weeks. A responder was defined as a patient with a ≥ 1 category improvement in WOMAC question A1 and no knee-related adverse events. The safety of repeat treatment (week 26) with Synvisc-One was assessed in all patients over a 4-week period. Acetaminophen rescue was permitted up to 48 hours before study visits.

Two medical studies involving a total of 132 patients were done in Germany. The patients in these studies were at least 40 years old and had knee pain due to OA. The patients were placed in one of two groups. One group was given an injection of SYNVISC into one or both knees once a week for three weeks. The second group was given an injection of salt water once a week for three weeks. As part of the study, knee joint pain was measured for 26 weeks. Also, patients and doctors were asked to judge the success of the treatment for 26 weeks. Patients with OA knee pain, who did not get pain relief with other medicines, got pain relief with SYNVISC. The patients given SYNVISC had more pain relief than the patients given salt water. Some patients started to feel pain relief after the first week of SYNVISC treatment. The most pain relief and the greatest amount of treatment success was seen 8 to 12 weeks after SYNVISC treatment started. A medical study done in the United States involved 90 patients. The patients were at least 40 years old and had knee pain due to OA. Patients were placed into one of two groups. One group was given SYNVISC once a week for three weeks. The second group had a needle inserted into the knee to have any fluid removed (this procedure is called arthrocentesis [pronounced AR-thro-sen-TEE-sis]) once a week for three weeks. Patients improved after SYNVISC treatment, but not more than patients who had arthrocentesis. This study was different from the German studies because the last time the two groups were compared was only two weeks after the last SYNVISC injection. The study was also different in other ways, including length of time that patients had to stop taking medicines before they could start treatment. The length of time patients had to stop taking medicines was two weeks in the German studies and, four weeks in the U.S. study.

2 STUDY RATIONALE

There is a lack of effective treatment for individuals including surgical options with mild osteoarthritis outside of physical therapy exercises, oral analgesic medications, and steroid injections which have possible negative side effects and short durations of symptom improvement. Hylan G-F 20 in a single injection form can provide analgesic benefit and can be used as a treatment in younger patients not improving with traditional treatments. This study is for research purposes only.

RISK / BENEFIT ASSESSMENT

Young patients with osteoarthritis are typically not surgical candidates. Randomized control trials for arthroscopy in arthritis patients do not show long term benefits. Patients want conservative treatment with low side effect profiles which can improve their quality of life. Hylan G-F 20 in a single injection form can provide analgesic benefit for patients with knee osteoarthritis. The treatment may reduce the need for oral medications and facilitate rehabilitation exercises. Patients may have better exercise tolerance with less pain. As shown in medical studies of patients with osteoarthritis (OA) of the

knee, where approximately half received a single injection of SYNVISC and the other half either had fluid removed from the knee and/or received injections of the same volume of salt water (a “Saline Control” injection), the major benefits of SYNVISC are pain relief and improvement in other symptoms related to OA of the knee.

STUDY OBJECTIVES

2.1 Primary Objective

There are two primary objectives to this study:

Specific Aim 1: To identify whether injection of 6 mL hylan G-F 20 decreases pain over 26 weeks in young (ages 30 to 50 years) active patients with symptomatic primary osteoarthritis of the knee not treated previously with hylan G-F 20.

Specific Aim 2: Though symptoms can be improved for periods up to 6 months, pain symptoms can recur. The effect of repeated treatments of hylan G-F 20 will be studied.

2.2 Secondary Objectives

There are two secondary objectives to this study:

Specific Aim 3: To identify the effects of treatment with hylan G-F 20 on activity levels (using objective activity measures utilizing accelerometer and Physical Activity Enjoyment Scale (PACES)) and quality of life scores (WOMAC, SF-12) comparing baseline to treatment at 3 months.

Specific Aim 4: is to understand the natural history of conservative treatment on this cohort of patients over a 3 year period.

3 STUDY DESIGN

3.1 Study Overview

This study aims to study use of viscosupplementation as a treatment of pain for young individuals who are active. Typically viscosupplementation is considered an intervention for knee osteoarthritis often for older patients who are less active. Many young active patients can also develop knee osteoarthritis after trauma or surgery or for congenital reasons. Treatment of these patients commonly are steroid injections which have more biologically detrimental effects for cartilage compared to viscosupplementation Synvisc One injections which are a single injection will be used to determine effectiveness of reducing pain and maintaining an active healthy lifestyle for younger patients aged 30-50 years old.

This study will be an open label longitudinal cohort study with natural history over 3 years. Screening data will be reviewed to determine subject eligibility. Subjects who meet all inclusion criteria and none of the exclusion criteria will be entered into the study. Subjects enrolled in the cohort will have baseline functional testing performed including a motion gait analysis, 12 minute walk test, and 3-day accelerometer data. Subjects will receive a single 6 mL intra-articular injection of hylan G-F 20 in the target knee at baseline. All ongoing treatments will be monitored at 6 month intervals over the 3 year

duration of the study. Patients can receive any other conservative treatments (e.g., oral medications, physical or other therapy, acupuncture, etc., except other injection treatments) and current treatments will be documented during each patient encounter. An initial injection of hylan G-F 20 will be injected in the symptomatic knee using a standard supine lateral approach using a 20 gauge needle. A face to face follow up visit will be carried out 6 months after first injection with additional face to face meetings every 6 months thereafter unless the subject requires an additional injection of hylan G-F 20. Hylan G-F 20 treatments can be administered up to three times each year during the study duration. After each injection, follow up measures will be carried out using secure e-mail or phone contact at 6 weeks, 12 weeks, 18 weeks after each in-office evaluation or injection. Follow up will consist of WOMAC, Lysholm score, and Tegner score. . Patients may return for retreatment of hylan G-F 20 if symptoms recur after at least 4 months following their previous injection and they meet the inclusion criteria for pain levels on the following WOMAC questions A1 (How much pain have you had walking on a flat surface?), C8 (How much difficulty have you had going down the stairs?), C9 (How much difficulty have you had when going up the stairs?), C10 (How much difficulty have you had when getting up from a sitting position?) and/or C23 (How much difficulty have you had while doing heavy household chores?). Inclusion criteria for pain level is defined by selecting moderate, severe, or extreme on all questions A1, C8, C9, C10 and/or C23. Those subjects who select mild or no pain levels on any of A1, C8, C9, C10 and/or C23, will not meet the criteria for WOMAC pain level and retreatment. Patients requiring three injections of hylan G-F 20 in 4 months or less will be allowed to exit the cohort after their six-month follow up following the third injection. Otherwise, patients will be followed until they reach the 3 year follow up, or drop out for other injection treatments or surgical treatment. Therefore, patients would potentially be able to receive up to 9 injections during the 3 year study.

Total time for the study will be approximately 8 clinical hours over 3 years, 21 days for the accelerometer test and 4.5 hrs of email/phone contact.

3.2 This experimental Synvisc-One indication is for the treatment of pain in osteoarthritis (OA) of the knee in patients who have failed to respond adequately to conservative non-pharmacologic therapy and simple analgesics (e.g., acetaminophen).

4 CRITERIA FOR EVALUATION

4.1 Primary Efficacy Endpoint

Co-Primary endpoints

- o Proportion of subjects reporting being in PASS during at least one Study Contact Point during entire 36 month study period
- o Proportion of Study Contact Points that each subject reports being in PASS during entire 36 month study period

Secondary endpoints

- o Change in scores over 36 months for:

- o Worst Knee Pain
- o Five KOOS domains
- o SF-12
- o 12-minute walk test
- o 3-day accelerometer test

The primary endpoint for the study will be analyzed using a responder analysis. The proportion of responders following injection within the 6 months following the baseline injection will be calculated based on Worst Knee Pain scores. A specific timeframe of interest will be the initial 6 months of treatment following the second and any subsequent hylan G-F 20 injection.

4.2 Secondary Efficacy Endpoints

- o Change in scores over 36 months for:
- o Worst Knee Pain
- o Five KOOS domains
- o SF-12
- o 12-minute walk test
- o 3-day accelerometer test

4.3 Safety Evaluations

Adverse reactions will be checked on all phone interviews and clinic visits. Adverse reactions will be captured and tabulated

The most commonly reported related local adverse events were transient, mild-to-moderate arthralgia, arthritis, arthropathy, injection site pain and joint effusion. No serious adverse events were reported in clinical trials in knees injected with Synvisc-One. Serious local adverse events have been reported only rarely in post-marketing use. Repeat treatment did not affect the safety profile. In the pivotal clinical trial, there was one related systemic event of syncope. The most common systemic side effects irrespective of relationship to Synvisc-One were headache, back pain, nasopharyngitis and influenza. Systemic adverse event profiles were similar between patients in the Synvisc-One and Saline Control groups.

5 SUBJECT SELECTION

5.1 Study Population

Subjects with a history of symptomatic unilateral primary or secondary knee OA for more than 6 months, who meet the inclusion and exclusion criteria, will be eligible for participation in this study.

5.2 Inclusion Criteria

Inclusion Criteria:

1. Male or female patients aged 30-50 years
2. History of symptomatic unilateral primary or secondary knee OA for more than 6 months

3. Signed written informed consent
 4. Radiographic evidence of Kellgren-Lawrence Grade I or II OA of the target knee
 5. Body Mass Index (BMI) < 30 kg/m²
 6. Activity criteria (Tegner score > 3)
 7. Continued target knee OA pain despite conservative treatment \geq 3 months (e.g., weight reduction, physical therapy, analgesics)
 8. Willing to withhold intake of NSAIDs (including COX-2 inhibitors) and analgesics, for a washout period of minimum 3 days up to 21 days prior to baseline visit (depending on medication)
 9. Willing to discontinue prohibited treatments and medications throughout study period
- Baseline inclusion criteria
10. Completed OA medication washout period
 11. Target knee pain 4-8 (0-10 NRS) during most painful knee movement (Worst Knee Pain)
 12. If female, must have had a negative urine pregnancy test and used a medically acceptable form of contraception for at least 1 month prior to baseline and agree to continued use of contraception for the duration of the study. Otherwise, females must be surgically sterile, or postmenopausal (as documented in medical history) for at least 1 year. The fetal safety profile for G-F 20 is unknown. Pregnancy will affect the individual's regular activity levels. Females who become pregnant during the study will be excluded from the study. Subjects who become pregnant will be followed up by telephone every 3 months to check for any adverse effects. They will also be recommended to follow routine obstetric visits. Males should be able to father children as it has no expected effects on activity levels.

5.3 Exclusion Criteria:

1. Known allergy to hylan G-F 20 or any of its components, or to avian proteins, eggs, feathers, down, or poultry
2. Clinically apparent tense effusion or other acute inflammation of the target knee at baseline
3. History of target knee viscosupplementation treatment
4. History of major surgery for OA in target knee including arthroplasty or tibial osteotomy
5. Arthroscopic surgery or intra-articular steroid injection in target knee within six months of baseline visit
6. Significant (as judged by the Investigator) alignment deformity of target knee
7. Ipsilateral symptomatic OA of hip or ankle; contralateral symptomatic OA of hip, knee, or ankle
8. History of:
9. Septic OA of any joint
10. Inflammatory arthropathy such as RA, gout, pseudogout, lupus, crystalline inflammatory arthropathy
11. Active infection of lower extremity
12. Known significant acute and/or concurrent medical disease including, but not limited to current malignancy, history of transplant surgery, congestive heart failure,

- significant unstable cardiovascular disease, renal hepatic pulmonary, endocrine, metabolic, or GI condition
13. Any known contraindication to acetaminophen
 14. Venous or lymphatic stasis in either leg
 15. Peripheral vascular disease
 16. Patient has been prescribed chronic opioid analgesics at time of baseline visit
 17. Concurrent multi-system or multi-limb trauma
 18. Patient plans to become pregnant during study period
 19. Patient plans to move significantly out of area, have surgery, or initiate or cease other OA treatments
 20. Knee pain improves during washout period
 21. Workman's Comp patient
 22. Written informed consent (and assent when applicable) obtained from subject or subject's legal representative and ability for subject to comply with the requirements of the study.
 23. Pregnant, breastfeeding, or unwilling to practice birth control during participation in the study.
 24. Presence of a condition or abnormality that in the opinion of the Investigator would compromise the safety of the patient or the quality of the data.

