6 CONCURRENT MEDICATIONS

All subjects should be maintained on the same medications throughout the entire study period, as medically feasible, with no introduction of new chronic therapies. Patients can receive any other conservative treatments (e.g., oral medications, physical or other therapy, acupuncture, etc., except other injection treatments) and current treatments will be documented during each patient encounter.

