6.1 Allowed Medications and Treatments

Patients can receive any other conservative treatments (e.g., oral medications, physical or other therapy, acupuncture, etc., except other injection treatments) and current treatments will be documented during each patient encounter.

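### Entry pain is scored after an analgesic washout but response is scored with usual analgesics allowed, so resuming a pre-study drug can count as response to the injection

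*Combined protocol and SAP*

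**What the plan says.** **Entry (section 5.2).** Criterion 8 asks for willingness to withhold NSAIDs and analgesics "for a washout period of minimum 3 days up to 21 days prior to baseline visit". The baseline criteria then list "Completed OA medication washout period" (criterion 10) next to "Target knee pain 4-8 (0-10 NRS) during most painful knee movement (Worst Knee Pain" (criterion 11). Criterion 7 requires "Continued target knee OA pain despite conservative treatment" but sets no score while on treatment. Exclusion 20 in section 5.3 removes subjects under "Knee pain improves during washout period"; nothing removes those whose pain rises off drug.

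**Follow-up.** Section 9 has Worst Knee Pain rated at the 6-, 12- and 18-week contacts and at the 6-month visit. No hold period before these ratings appears in section 9 or Appendix 1. Section 6.1 states: "Patients can receive any other conservative treatments (e.g., oral medications, physical or other therapy, acupuncture, etc., except other injection treatments". Section 6 adds: "All subjects should be maintained on the same medications throughout the entire study period, as medically feasible". The synopsis entry for prohibited medications names no drug.

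**Analysis (section 13).** Response is a score of 3 or less. One paragraph requires it to be maintained throughout the 6 months; another counts response within the 6 months. Neither the definition nor the missing-data rule uses analgesic intake. Success requires the 95% interval for the response rate to exclude 0.50.

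**The concern.** The score that admits a subject is an off-drug score, while the score that makes the subject a responder may be an on-drug score. Take a subject at 3 on a usual NSAID and 5 after washout. That subject is eligible, receives the injection, resumes the NSAID, returns to 3 and counts as a responder although the injection did nothing. No new co-treatment is needed: the drug stopped for washout is the subject's usual one, and section 6 asks that medications stay the same.

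Aim 1 asks whether the injection decreases pain, and the study is single-arm and open-label. The shift can only raise the response rate, and no concurrent group reveals it.

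**Working it through.** **1. The plan's own figure.** The section 13 power table gives 92% for n=120 at a true rate of 0.65. The Wilson lower limit is

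L = [p + z²/(2n) − z√(p(1−p)/n + z²/(4n²))] / (1 + z²/n), with z = 1.96.

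At 70/120, L = 0.494; at 71/120, L = 0.502. Success therefore needs at least 71 responders, or 59.2%. The exact binomial chance of 71 or more is 92.3% at 0.65 (plan: 92%) and 61.2% at 0.60 (plan: 61%). The arithmetic is sound; the issue is what is counted as a response.

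**2. Illustration with no injection effect.** The documents give no off-drug pain distribution, drug effect or resumption share, so all of these are assumptions:
- off-drug pain T is normal with mean 5.5 and SD 1.5;
- each rating is T − d·R + e, rounded and kept within 0-10, where e has SD 1, d is the drug effect and R = 1 if the subject has resumed;
- the entry rating, off drug, must be 4-8 (document);
- four follow-up ratings in 6 months, response at 3 or less (document).

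Simulated shares of responders, in percent:

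| Drug effect d | Week 26 | Any of four | All four |
|---|---|---|---|
| Nobody resumes | 8.2 | 20.8 | 0.8 |
| 1, all resume | 22.9 | 46.0 | 5.4 |
| 1.5, all resume | 33.6 | 60.0 | 11.1 |
| 2, all resume | 45.8 | 72.8 | 19.8 |

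**3. Partial resumption.** If a share s resumes at every rating, the rate is (1−s) × off-drug rate + s × all-resume rate. With s = 0.5 it is the average of the two:
- week 26: 15.6, 20.9 and 27.0 for d = 1, 1.5 and 2. For example, (8.2 + 45.8)/2 = 27.0;
- any rating: 33.4, 40.4 and 46.8;
- all four: 3.1, 6.0 and 10.3.

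**4. Comparison with 0.50.** With half resuming, no reading reaches 0.50. With all resuming, only the any-rating reading does, and only for d of about 1.5 or more. The share needed to bring that reading to 0.50 is:
- d = 1.5: (50 − 20.8)/(60.0 − 20.8) = 29.2/39.2 = 74%;
- d = 2: (50 − 20.8)/(72.8 − 20.8) = 29.2/52.0 = 56%.

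To reach the 59.2% observed rate that passes at n=120:
- d = 1.5: 38.4/39.2 = 98%;
- d = 2: 38.4/52.0 = 74%.

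At week 26 the highest rate, about 46%, passes with probability 0.3%. The throughout reading never exceeds 20%.

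**The case against.** **The benchmark already includes background care.** The 70% reference is a rate on appropriate care plus hylan G-F 20 (section 13.6), and the primary test uses an absolute rate, not a change from baseline. On-drug follow-up is therefore closer to the benchmark than drug-free follow-up would be. This stands, and it rules out testing a drug-free response against 0.50. It does not separate an injection effect from drug resumption, and the documents do not say whether the reference study used a washout.

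**A reader might infer that the trial would probably succeed falsely.** The documents do not support that. They give no figure for analgesic use, and the large figures above need most or all subjects to resume an effective drug at every rating. One could also add resumption to the 38% appropriate-care rate: (0.50 − 0.38)/(1 − 0.38) = 19% of the remaining subjects would then bring the rate to 0.50. But 38% is itself a rate on appropriate care, so this may count the same medication twice.

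**A reader might infer that every change from baseline is affected.** Appendix 1 places KOOS, WOMAC, SF-12, the walk test and the accelerometer at screening, 1-3 weeks before treatment, and none at Visit 1. Their washout status is unclear. Even Worst Knee Pain appears at screening and not at Visit 1, although criteria 10 and 11 pair it with a completed washout.

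**Resumption is only one reading.** Criterion 9 and section 12 presuppose prohibited medications, yet none is named. That is a reason to reconcile the text; it does not close the gap.

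**Medication data exist.** Section 8.1.1 captures doses and dates at visits, and the contacts ask about other treatment. Timing of the last dose relative to a rating is the only item missing.

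**The cited saline-controlled trial.** Section 1.2 reports "Acetaminophen rescue was permitted up to 48 hours before study visits". This describes another study and covers acetaminophen only. It shows that analgesic timing before a rating can be specified, and no more.

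**Conclusion.** The asymmetry is in the text and no rule in the plan removes it. A subject can follow the protocol exactly and be counted as a responder through drug resumption alone. The direction is favourable and there is no control.

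The size is unknown. Under the stated assumptions, with a drug effect of 1 to 2 points, week-26 response rises from 8% to 23-46% (all resume) or 16-27% (half resume). Any-rating response rises from 21% to 46-73% or 33-47%, and all-four response from 1% to 5-20% or 3-10%. Resumption alone exceeds 0.50 only on the any-rating reading, with a drug effect of about 1.5 points or more and most subjects resuming. For 1.5 points, resumption must be nearly universal to reach the passing count. On the throughout reading it inflates the rate without approaching 0.50.

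The point applies to the pain score used for entry. It should be fixed because last-dose timing cannot be reliably reconstructed later. It does not show that the trial's conclusion would be wrong.

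**What to change.** 1. With each Worst Knee Pain rating, including the 6-, 12- and 18-week contacts, record which NSAID or analgesic was last taken and the date.
2. Prespecify a sensitivity analysis of the primary response. Show the rate by analgesic use at the rating, and the rate when scores of 3 or less taken within a stated analgesic window do not count. Report each as an estimate with a 95% interval, not as a second pass/fail test against 0.50, since that threshold derives from a rate on hylan plus appropriate care.
3. Word the primary conclusion as response on hylan G-F 20 plus permitted usual analgesics. Make no injection-alone claim; a single-arm open-label study cannot support one even if the sensitivity rate is high.
4. Reconcile the synopsis concomitant-medication entry and sections 5.2, 6, 6.1 and 12 on medication during the study and on conditions at assessment. No medication rule is proposed here.

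Cost: one question per contact and one extra analysis. The sensitivity rate will be lower, and conservative for regular analgesic users: someone who keeps to a daily NSAID as section 6 asks could not count as a responder in it, however well the injection worked.
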